Authors must describe what they contributed, and editors must publish such information. All others who contributed to the work who are not authors should be named in the acknowledgments, and what they did should be written.

## **Introduction**

Miscarriage is defined by the World Health Organization as the interruption of the pregnancy up to 20-23 weeks, or the products of pregnancy weighing less than 500 grams (1). Nearly 15% of known pregnancies end in miscarriage, especially in the first 12 weeks. Estimates indicate that 68000 women die worldwide each year, as a result of unsafe abortions. Abortions are the major cause of maternal death, particularly in Latin America and the Caribbean. In cases of retained and incomplete abortions, uterine emptying is recommended. In the first trimester of pregnancy, either pharmacological or surgical procedure is accepted according to international guidelines.

Pharmacological treatment for uterine evacuation includes the administration of mifepristone and misoprostol or misoprostol alone. Nevertheless, surgical methods have been shown a greater acceptability and patient satisfaction due to a reduced incidence of adverse effects. Currently, Manual Vacuum Aspiration (MVA) is the technique recommended by the Brazilian Ministry of Health and the Brazilian Federation of Gynecology and Obstetrics.

MVA should be performed after cervical ripening. This pre-surgical procedure makes the procedure safer and more effective. In Brazil, misoprostol is the most suitable drug to be used in these cases because of its efficacy, ease of use, low cost, stability at room temperature, and availability. Misoprostol is a synthetic prostaglandin E1 analog and can be administered by oral, sublingual, buccal, rectal, and vaginal routes.

Smaller doses, such as 200 µg, have not yet been tested enough in the literature, being a potential research line. Therefore, the objective of this study is to evaluate a Misoprostol dose of 200 µg compared to his standard dose of 400 µg.

## **JUSTIFICATION FOR THE PROJECT**

The studies currently available in the literature are not conclusive as to whether there is greater efficacy in uterine cervical priming using misoprostol 200 µg compared to 400 µg. A prospective study will bring more information for further decision.

## **STUDY GOALS**

### **Primary**

To verify if a dose of 200 µg of misoprostol results in a cervical priming is not

less than 25% at the dose of 400 µg usually used.

## **Secondary**

To verify if there is a relationship between the dose of misoprostol and the degree of cervical dilation ( $\geq 8\text{mm}$  /  $<8\text{mm}$ ).

## **HYPOTHESIS**

Our null hypothesis is that  $P_{\text{standard (400µg)}} \geq P_{\text{alternative (200µg)}} + 25\%$ ;

Our alternative hypothesis is that  $P_{\text{standard (400µg)}} - 25\% < P_{\text{alternative (200µg)}}$ .

## **Variables:**

1. The control group (400 µg misoprostol);
2. The experimental group (200 µg misoprostol);
3. Cervical dilation present or not.

## **METHODS**

### **Study design**

This will be a triple-blinded, non-inferiority, two-arm parallel randomized clinical trial (RCT) at Hospital de Clínicas de Porto Alegre (HCPA), following the parameters of CONSORT.

### **Geographical and temporal limitation**

The study will be carried out in patients seen at the gynecological emergency of HCPA. A period of 48 months will be allowed for data collection (5 cases of abortion per week).

### **Inclusion criteria**

All patients presented at the HCPA gynecological emergency unit, aged between 18-50 years old, with an indication for manual vacuum aspiration (MVA) and the use of misoprostol, <12 weeks of gestation, without comorbidities will be invited.

## **Exclusion criteria**

Patients who do not wish to participate in the project, have an ectopic pregnancy, with comorbidities (congestive heart failure, chronic obstructive pulmonary disease), with hypovolemic shock, with istmocervical insufficiency, who have an infection (fever, pus, leukocytosis [ $> 14000$  leuc]), with a twin pregnancy, Marfan syndrome, allergic to misoprostol, with blood dyscrasia, who have an pervious cervical canal at the time of the consultation, those with previous surgery of the uterine cervix (conization) and concomitant use of IUDs will be excluded.

## **Randomization**

Patients eligible for this study will be invited to participate in the research. After reading and signing the informed consent, patients will be submitted to a standardized interview and will be randomized to one of the two arms.

Patients will be randomly allocated to receive misoprostol 400 or 200  $\mu$ g. Randomization list was obtained from a web-based site ([www.randomization.com](http://www.randomization.com)) and divided into blocks of four. The randomization sequence will remain in sealed, opaque, sequential envelopes.

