## **Treatment**

After randomization, one of the assisting researchers, one that will not perform the MVA procedure, will introduce the misoprostol into the vagina. A 200  $\mu$ g misoprostol tablet will be inserted into the vaginal fornix. For reducing bias, a second mock introduction will performed in the 200  $\mu$ g group. The 400 $\mu$ g group will have a double insertion. Medical staff that will perform the MVA will not be aware of the randomization.

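### A fixed block size of four at one site, with an inserting researcher who must know the arm and is not barred from recruiting, could let up to one third of allocations be predicted with certainty

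*Combined protocol and SAP*

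**What the plan says.** - **Randomization:** the list came from a web-based generator and is "divided into blocks of four". No other size and no stratification is described. Concealment rests on envelopes: "The randomization sequence will remain in sealed, opaque, sequential envelopes". Patients are randomized after consent and an interview.
- **Geographical and temporal limitation:** there is one site. "The study will be carried out in patients seen at the gynecological emergency of HCPA".
- **Treatment:** "one of the assisting researchers, one that will not perform the MVA procedure, will introduce the misoprostol into the vagina". The 200 µg arm receives one tablet and a mock second insertion; the 400 µg arm receives two real insertions. "Medical staff that will perform the MVA will not be aware of the randomization".
- **Inclusion criteria:** every patient who meets the criteria is to be invited.
- **Study design:** the trial is called triple-blinded, but the three parties are not named.

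The documents do not say who screens and invites patients, who opens the envelopes, how many researchers insert the drug, who knows the block size, or whether the analyst is masked.

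**The concern.** Opaque envelopes hide the next assignment from someone who has no other information. They do not hide it from someone who has seen the earlier assignments in the block and knows that each block holds two of each arm. The inserter learns the arm of every patient she or he treats, and the block size is printed in the protocol. The only restriction on this role is that the inserter does not perform the aspiration.

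If that person also screens or invites patients, or tells someone who does, enrolment can be influenced by knowledge of the next arm. There is room for judgement at that stage. A cervix that is already open at consultation is an exclusion, and the data form records it as 4 mm dilation. That finding is closely related to the outcome, so lenient or strict application according to the expected arm could shift the comparison. Masking the aspiration operator does not help here, because this selection happens before randomization.

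**Working it through.** **Inputs.** Two arms and blocks of four (Randomization); one site, taken as one sequence; 96% and 86% expected, margin 25 points, one-sided 2.5%, 95% power, N = 184 (Sample size). The allocation ratio is not stated. 1:1 is assumed, which fits 184 = 2 × 92 and gives 46 complete blocks.

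**The plan's own figure.** n per arm = (1.960 + 1.645)² × (0.96 × 0.04 + 0.86 × 0.14) / (0.25 − 0.10)² = 12.995 × 0.1588 / 0.0225 = 91.7, so 92 per arm and 184 in total. This reproduces, and nothing below changes it.

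**Certain predictions with fixed blocks of four.** There are six equally likely sequences. AABB and BBAA each make positions 3 and 4 certain (2 allocations). The other four make only position 4 certain (1 allocation).

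- Share certain = (2 × 2 + 4 × 1) / (6 × 4) = 8/24 = 33.3%, or about 61 of 184.
- Best-guess accuracy by position is 1/2, 2/3, 2/3 and 1, with mean 70.8% (about 130 of 184), against 50% by chance.

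Both figures require an observer who knows the block size and boundaries and has seen every earlier allocation in the block.

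**Several inserters.** Suppose k inserters share cases at random and exchange nothing. An allocation is certain to a given inserter only if that person treated both earlier patients in the arm that is already full, which has probability 1/k². The share is 1/(3k²):

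- k = 1: 33.3% (about 61 of 184)
- k = 2: 8.3% (about 15)
- k = 3: 3.7% (about 7)

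Simulation agrees with the formula.

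**Randomly varying blocks.** The simulated observer knows all earlier allocations and the set of possible sizes, but not the size of each block. Sizes 4 and 6 give about 5.5% certain and 69% best guess. Sizes 4, 6 and 8 give about 2.2% certain (about 4 of 184) and 68% best guess.

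**Illustration of what selection could do.** Assumptions: the true rates lie on the margin (96% vs 71%); the observer influences enrolment and uses every certain 200 µg slot; each patient so chosen has a 10-point higher chance of success; 400 µg patients are unaffected. The 8 certain slots split 4 and 4 between the arms, and each arm holds 12 of the 24 places, so one third of 200 µg patients are affected. The bias is 10 × 1/3 = 3.3 points. False non-inferiority is the exact binomial probability, with 92 per arm, that the upper 95% limit lies below 25 points. The plan names no interval method, so Newcombe and Wald are both shown.

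| Case | 200 µg rate | Newcombe | Wald |
|---|---|---|---|
| No selection | 71.0% | 2.6% | 3.0% |
| Fixed 4, one observer | 74.3% | 9.7% | 11.1% |
| Fixed 4, two inserters, no sharing (10 × 1/12 = 0.8 points) | 71.8% | 3.7% | 4.3% |
| Fixed 4, three inserters, no sharing (10 × 1/27 = 0.4 points) | 71.4% | 3.0% | 3.5% |
| Random 4/6/8, one observer | 71.2% | 2.8% | 3.3% |

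With a 5-point effect in place of 10, the one-observer case gives 5.2% to 6.0%.

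**The case against.** **One third is a maximum.** This stands. The Treatment section speaks of one among the assisting researchers, which allows the task to be shared, and the share falls quickly with each further inserter who keeps allocations to themselves. However, the plan neither fixes the number of inserters nor forbids sharing.

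**The protocol invites everyone eligible.** On paper this leaves no choice over whom to approach, and nothing says that the inserter recruits. A reader might infer from the design that recruitment is or will be selective; the documents do not support that. They also describe no step that would enforce the rule, and judging whether the cervix is already open leaves some latitude.

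**The 10-11% error rate stacks assumptions.** This stands too. It needs a single observer, influence over enrolment, use of every opportunity, a sizeable gain each time and a true difference exactly at the margin. It is a worst-case illustration, not an estimate.

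**Varying the blocks adds little once roles are separated.** This stands in part. Best-guess accuracy falls only from 71% to 68%, and varied blocks do not mask the inserter. The role restriction does most of the work. Varied blocks remove nearly all certain predictions, which helps if that restriction is not kept.

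**Blinding is not contradicted.** A reader might infer that blocks of four undermine the triple-blinded label, or that outcome assessment is compromised. Neither follows. Block size bears on allocation concealment. The aspiration staff, who presumably measure dilation, are stated to be unaware of the arm, and the data form records a treatment number, not a dose, which is at least consistent with coded data.

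**Conclusion.** The concern holds as an avoidable weakness in allocation concealment. A fixed, published block size at one site, together with an inserter who must know the arm and is not barred from recruiting, allows up to 33% of allocations (about 61 of 184) to be predicted with certainty by one fully informed observer. The figure is about 8% or 4% for each of two or three inserters who do not share information. This assumes 1:1 allocation and knowledge of the block size and boundaries. Bias would follow only if that knowledge reached enrolment decisions; the documents leave this open and do not show it. The sample size is unaffected.

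Separately, and as a minor point, the triple-blinded label is undefined. The documents show masking only of the patient (by the mock insertion) and of the aspiration staff. That gap would exist under any block scheme.

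**What to change.** 1. **Randomization:** use permuted blocks of randomly varying size, for example 4, 6 and 8, generated by someone outside the recruiting team. Do not disclose the sizes to recruiters, which includes leaving them out of the protocol copy they hold. If enrolment has begun, apply this to the remaining envelopes. State who opens the envelopes.
2. **Treatment:** state that inserting researchers do not screen, invite or consent patients, do not record outcomes, and do not disclose allocations.
3. **Study design (minor):** name the blinded parties. Either describe a third, such as an analyst working with coded arms until the analysis is locked, or limit the claim to the patient and the aspiration staff.

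The cost is a new list, new sealed envelopes and a few sentences. With blocks of up to 8, the arms could differ by up to 4 patients if enrolment stops mid-block. The role restriction requires that a different team member handles recruitment on each occasion.

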## **Treatment**

After randomization, one of the assisting researchers, one that will not perform the MVA procedure, will introduce the misoprostol into the vagina. A 200  $\mu$ g misoprostol tablet will be inserted into the vaginal fornix. For reducing bias, a second mock introduction will performed in the 200  $\mu$ g group. The 400 $\mu$ g group will have a double insertion. Medical staff that will perform the MVA will not be aware of the randomization.

## **Outcomes**

The following outcomes will be determined:

1. Dilatation of the cervix without the need for a dilator between 3 and 6 hours after placing the misoprostol;
2. Dilatation of the cervix with 8mm. The measurement of cervical dilation will be done with a Karmann cannula, starting with the largest diameter (11 mm) and decreasing until it was possible to introduce, without resistance, the cannula into the uterine cavity (continuous variable 4 to 11).

## **Sample size**

The sample size was calculated as a non-inferiority clinical trial according to the literature (Blackwelder 1982). We expected that cervical dilation would be achieved in 96% of the cases using 400 µg of misoprostol and 86% in the 200 µg group. If there is a true difference in favour of the 400 µg treatment of 10% (96% vs 86%), then at least 184 patients were required in order to be 95% sure that the upper limit of a one-sided 97.5% confidence interval (or equivalently a 95% two-sided confidence interval) would exclude a difference in favour of the standard group of more than 25%.

The determination of non-inferiority margins was based on the literature (Hahn 2012; Wu et al. 2017; Kapp et al. 2010; Singh et al. 1998). It is known that 400 µg of misoprostol yields a 96% cervical dilation > 8 mm (Singh et al. 1998). We considered 86% of the 200 µg misoprostol group as the minimal acceptable percentage. The non-inferiority margin was determined by  $\frac{1}{3}$  of the difference between the 400 µg effect (96.7%), compared to the 200 µg dose (23.3%) found in the literature, i.e.  $73.4 / 3 = 24.46$ . (Fong, Singh, and Prasad 1998; Hahn 2012; Wu et al. 2017; Kapp et al. 2010; Singh et al. 1998).

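### The 95% power stated for 184 patients is a normal-approximation figure; enumeration gives about 90 to 93%, depending on a confidence interval that the plan does not name

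*Combined protocol and SAP*

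**What the plan says.** All the planning inputs are in the Sample size section of the combined protocol and SAP.

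- Method: "The sample size was calculated as a non-inferiority clinical trial according to the literature (Blackwelder 1982").
- Rates: "We expected that cervical dilation would be achieved in 96% of the cases using 400 µg of misoprostol and 86% in the 200 µg group".
- Success criterion: the interval "would exclude a difference in favour of the standard group of more than 25" percentage points, judged on "the upper limit of a one-sided 97.5% confidence interval (or equivalently a 95% two-sided confidence interval").
- Result: "at least 184 patients were required in order to be 95% sure that the upper limit of a one-sided 97.5% confidence interval" will meet this criterion.

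The section does not say how the interval will be computed and reports no exact or simulated power. The Statistical analysis section lists a t-test, correlation tests and a chi-square test. It contains no confidence interval for a difference in proportions.

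**The concern.** The statement gives the probability of one defined event: the upper 95% limit falling below 25 points when the true rates are 96% and 86%. That probability can be computed exactly once an interval is chosen. The formula behind 184 approximates it by treating the difference in observed proportions as normal, with its variance fixed at the planning value. With a control rate close to 100% and fewer than four expected failures in that arm, the approximation may be optimistic.

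What is at stake is modest. Readers are told that the risk of missing non-inferiority under the planning assumptions is 5%. If the true risk is larger, the stated assurance should say so. The choice of interval, which the plan leaves open, then affects both the power and the error rate.

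**Working it through.** **Inputs** (Sample size section unless noted)

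- Rate on 400 µg: 0.96. Rate on 200 µg: 0.86. True difference: 0.10.
- Margin: 0.25.
- One-sided alpha: 0.025 (z = 1.960). Power: 95% (z = 1.645).
- Total: 184. The allocation ratio is not stated in words; 92 per arm is assumed from the two arms and the blocks of four in the Randomization section. All 184 are taken as evaluable.

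**1. Reproducing the plan's figure**

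Variance terms: 0.96 × 0.04 = 0.0384 and 0.86 × 0.14 = 0.1204, sum 0.1588.

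n per arm = (1.960 + 1.645)² × 0.1588 / (0.25 − 0.10)² = 12.996 × 0.1588 / 0.0225 = 91.7, rounded up to 92, so 184 in total.

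Formula power at 92 per arm: the standard error is √(0.1588 / 92) = 0.0415; 0.15 / 0.0415 − 1.960 = 1.65; Φ(1.65) = 95.06%.

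The plan's 184 and 95% both reproduce.

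**2. How thin the data are**

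Expected failures: 92 × 0.04 = 3.7 on 400 µg and 92 × 0.14 = 12.9 on 200 µg.

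**3. Enumerated power**

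For every pair of success counts (x₁, x₂), the binomial probability of x₁ out of 92 at 0.96 is multiplied by that of x₂ out of 92 at 0.86. These products are summed over all pairs whose upper 97.5% limit for the difference (400 µg minus 200 µg) is below 0.25.

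| Interval | Enumerated power | Short of 95% by | One-sided error at 96% vs 71% |
|---|---|---|---|
| Wald | 93.2% | 1.8 points | 3.0% |
| Newcombe | 91.1% | 3.9 points | 2.6% |
| Farrington-Manning score | 90.4% | 4.6 points | 2.3% |

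The last column is the probability of wrongly declaring non-inferiority when the true difference equals the margin with 400 µg at its planning rate (nominal 2.5%).

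The intervals differ because single patients move the decision. With 88 of 92 successes on 400 µg, Wald and Newcombe need at least 74 successes on 200 µg and the score interval needs 75. With 90 of 92, Wald needs 75 and the other two need 76.

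**4. What an enumerated 95% would take**

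The first sizes that reach it are 101 per arm (202) with Wald, 109 (218) with Newcombe and 111 (222) with the score interval. These are for scale only; more patients are not being asked for.

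**The case against.** The strongest reply is that the plan names a standard method and applied it correctly. The interval that matches the formula's unpooled variance is Wald, and on that basis the gap is only 1.8 points. The larger gaps arise only with intervals that the plan never mentions. This stands. A reader might infer that 184 is miscalculated, or that the risk of missing non-inferiority is about twice the stated 5%. The documents support neither: 184 is right for the cited formula, and the miss rate is 6.8% with Wald, reaching 8.9 to 9.6% only with Newcombe or the score interval.

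A second reply is that no interval is best everywhere. This also stands. Newcombe holds the error closer to nominal than Wald at 96% vs 71% (2.6% against 3.0%), but the order reverses at 90% vs 65% (2.7% against 2.6%). So Newcombe cannot be prescribed on error control in general.

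A third reply is that the gap is small beside the uncertainty in the assumptions. One point either way on the 200 µg rate moves Newcombe power to 94.8% (at 87%) or 86.1% (at 85%), and the section itself presents 86% as a minimum acceptable value. That limits the weight of the point but does not make the 95% correct at the stated rates.

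It is also tempting to pair the 96.7% used in the margin derivation with 86% and report a larger shortfall. That is not a fair test: it widens the true difference to 10.7 points, whereas the power statement specifies 10. Keeping 10 points (96.7% vs 86.7%) raises power to 94.4% with Wald and 92.1% with Newcombe. The section uses 96% throughout its power statement and 96.7% only as a literature input to the margin.

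**Conclusion.** The point holds as a minor correction. At the plan's own rates and margin, none of the three intervals in the table delivers 95%: the enumerated power is 93.2%, 91.1% or 90.4%. The documents do not settle which figure applies, because no interval is named for the decision.

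The result rests on 92 evaluable patients per arm, true rates of 96% and 86%, the stated 25-point margin and no continuity correction (with one, Wald and Newcombe fall to about 89%). It should not be read as showing that the trial is inadequately sized. Power stays at about 90% or more with the three intervals under the planning assumptions.

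**What to change.** Keep 184 patients. In both the Sample size and the Statistical analysis sections, name the two-sided 95% interval for the difference in proportions that decides non-inferiority. A score interval is a reasonable choice, since it holds the one-sided error at 2.3% at 96% vs 71%; its price is the lowest power of the three.

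Then replace the 95% with the enumerated figure for the chosen interval at 184 evaluable patients: about 90% (score), 91% (Newcombe) or 93% (Wald). For example: with 92 evaluable patients per arm and true rates of 96% and 86%, the probability that the upper limit of the two-sided 95% Farrington-Manning score interval lies below 25 percentage points is about 90%, by enumeration of the binomial outcomes.

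The cost is wording only. No patient, margin or decision threshold changes; the stated power becomes slightly less favourable.

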## **Statistical analysis**

Statistical analysis to be used will be performed using Student's *t*-Test, after confirming the normal distribution of the sample, otherwise, a mathematical transformation of the data will be performed to obtain a Gaussian curve. If there is no statistical difference between the groups, cervical dilation between each group can be verified with the Pearson (or Spearman) test using the continuous variables of both groups (dilation), or the chi-square test dilation <8, ≥8mm. If there is a statistical difference between the groups, the correlations will be by groups, i.e., 400 µg and 200 µg.

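### The analysis section never applies the 25-point non-inferiority criterion, and on the design assumptions 200 µg will most probably meet that criterion while also testing statistically worse

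*Combined protocol and SAP*

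**What the plan says.** The Study design section declares a non-inferiority trial. In the Hypothesis section the null is that 400 µg is better by at least 25 points and the alternative is that any deficit is smaller. The Sample size section turns this into a criterion: the upper limit of a one-sided 97.5% interval, treated as equivalent to a two-sided 95% interval, "would exclude a difference in favour of the standard group of more than 25" per cent.

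The same section does not assume that the doses are equal. It states "We expected that cervical dilation would be achieved in 96% of the cases" on 400 µg and in 86% on 200 µg, "then at least 184 patients were required" "in order to be 95% sure" of meeting the criterion. It also describes 86% as the lowest rate it would accept for 200 µg.

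The Statistical analysis section names Student's t-test, correlation tests and a chi-square test for dilation below 8 mm versus 8 mm or more. It branches on whether the groups differ statistically. If they do not, dilation is examined by correlation or chi-square. The other branch reads "If there is a statistical difference between the groups, the correlations will be by groups". The section mentions no margin, no confidence interval and no non-inferiority conclusion, and it states no significance level.

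**The concern.** A test of difference asks whether the deficit is zero. The Hypothesis section asks whether it is below 25 points. No result of the first test, significant or not, answers the second question.

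The gap might be harmless if the two questions usually led to similar wording. They do not here, because an assumed 10-point deficit is paired with a 25-point margin. The interval the plan should expect is centred near 10, with both limits clear of 0 and of 25. An analyst who follows the Statistical analysis section would then report that the doses differ and stop. One who follows the Sample size section would report non-inferiority, and nothing in the plan requires the demonstrated deficit to be stated beside it. Either report gives half of the result, and the plan does not fix in advance how the two halves are presented together.

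**Working it through.** **Inputs.** From Sample size: rates 0.96 and 0.86, margin 0.25, one-sided 2.5% (two-sided 95% interval), 95% power, total 184. From Randomization: two arms, with the list "divided into blocks of four". No ratio is stated, so 1:1 (92 per arm) is assumed. Statistical analysis gives no level, so two-sided 5% is assumed for the tests of difference.

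**1. The plan's own figure.** With the unpooled normal formula,

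n per arm = (z₀.₉₇₅ + z₀.₉₅)² × [p₁(1−p₁) + p₂(1−p₂)] / (margin − difference)²

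= (1.960 + 1.645)² × (0.0384 + 0.1204) / (0.25 − 0.10)² = 12.995 × 0.1588 / 0.0225 = 91.7.

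This rounds up to 92 per arm, 184 in total. The stated figure is reproduced exactly.

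**2. Where the interval should fall.** The standard error is √(0.1588/92) = 0.0415, so the half-width is 1.96 × 4.15 = 8.1 points. The upper limit is below 25 when the observed difference is below about 25 − 8.1 = 16.9. The lower limit is above 0 when the observed difference exceeds about 8.1. With a true difference of 10, the chance of landing between 8.1 and 16.9 is about Φ(1.65) − Φ(−0.45) = 0.95 − 0.33 = 0.62.

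**3. Exact enumeration.** All 93 × 93 outcome tables for Binomial(92, 0.96) and Binomial(92, 0.86) were classified. Percentages are of trials.

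| Upper limit < 25 by | 200 µg worse by | Both | Non-inferior, not worse | Worse, non-inferiority not shown |
|---|---|---|---|---|
| Wald | Wald lower limit > 0 | 62.8 | 30.4 | 6.8 |
| Wald | Pearson chi-square | 62.0 | 31.1 | 6.8 |
| Newcombe | Pearson chi-square | 60.0 | 31.1 | 8.9 |
| Newcombe | Newcombe lower limit > 0 | 56.4 | 34.7 | 8.9 |
| Wald | Fisher | 52.0 | 41.2 | 6.8 |
| Wald | Continuity-corrected chi-square | 49.7 | 43.5 | 6.8 |

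A t-test on the 0/1 outcome, with the Wald limit, gives the same figures as the second row. The criterion is met in 93.2% of trials (Wald) or 91.1% (Newcombe), and Pearson's test finds 200 µg worse in 68.9%. The joint result is the most frequent in every row. The first and fourth rows need only the two-sided 95% interval that Sample size already specifies, with no assumed test or level. With the derived margin of 24.46 points in place of 25, the second row's joint figure is 60.8%.

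**4. The expected table.** 88/92 versus 79/92 is 95.7% versus 85.9%, a difference of 9.8 points with standard error 4.2. The 95% interval is 1.5 to 18.0 (Wald) or 1.3 to 18.7 (Newcombe), and the uncorrected chi-square p is 0.022. It is below 25 and above 0.

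**5. If 86% is a floor and not the expected rate.** With 400 µg at 96% and the second row's method, the joint result occurs in 51% of trials when the true 200 µg rate is 88%, 35% at 90% and 19% at 92%. At 90% it is no longer the most likely result.

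**6. What this does not cover.** The t-test in Statistical analysis seems meant for dilation in millimetres, for which the documents give no mean or SD. The percentages above are for the binary outcome only.

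**The case against.** The strongest reply is that the documents already settle the conclusion. Study design, Hypothesis and Sample size together make an interval of 1.5 to 18.0 a rejection of the null, which is non-inferiority. That stands. The alternative hypothesis allows a deficit below 25 points, and the design assumes one.

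A reader might infer that Sample size and Statistical analysis give contradictory verdicts on the same data. The documents do not support that reading. Worse than 400 µg, but by less than 25 points, is one coherent description of one interval. Nor does Statistical analysis set up a rival rule: its chi-square test appears only in the branch for no statistical difference, and a significant difference only changes how correlations are run. What remains is that the section naming the analyses omits the one that tests the hypothesis, and that no section says how a simultaneous deficit is reported.

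A reader might also infer that non-inferiority should be withheld whenever the lower limit exceeds 0. That would change the hypothesis. At the design assumptions, the chance of an unqualified claim would fall from 93.2% to 30.4% (Wald), in a trial sized for 95%. Disclosing both limits achieves the purpose without that cost.

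Finally, the size of the overlap is conditional on a true rate of 86%, which Sample size calls both its expectation and its minimum. That also stands, and is why the figure is given as a range.

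**Conclusion.** The concern holds as a gap between the stated hypothesis and the stated analysis. Hypothesis and Sample size define a criterion that Statistical analysis never applies, and the planned tests of difference cannot stand in for it. On the plan's own assumptions the most likely result, in about 50% to 63% of trials, is that 200 µg meets the 25-point criterion and is also statistically worse. A test of difference alone would then leave the primary question unanswered, and a bare statement of non-inferiority would leave out the deficit.

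The size rests on 1:1 allocation, 92 analysed per arm, the binary outcome, a two-sided 5% level for the tests, and true rates of 96% and 86%. If the true 200 µg rate is 90% it drops to about 35%. The mismatch between hypothesis and analysis depends on none of these assumptions.

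**What to change.** In Statistical analysis:

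- Make the primary analysis the two-sided 95% confidence interval for the 400 µg minus 200 µg difference in the binary dilation outcome. State which binary outcome is meant, since Outcomes lists dilatation without a dilator first while Sample size ties its 96% to dilation above 8 mm. Name the interval method.
- Conclude non-inferiority within 25 points if the upper limit is below 25, and that it was not shown otherwise.
- Give the test of difference no role in the primary conclusion.
- Report the margin and both limits with the verdict. Where the upper limit is below 25 and the lower limit is above 0, state in the same conclusion that 200 µg was statistically less effective, by less than 25 points.

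This leaves the hypothesis, margin and sample size as they are. It costs a few lines of text and no patients or data. The downside is a less favourable headline whenever the lower limit exceeds 0, which at the design assumptions is in most trials.
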